8.0 Consent Process

At the beginning of each participant's study participation, prior to the medical/neurological screening, the clinical research coordinator will meet a potential participant at MUSC, explain the proposed study, answer questions, and obtain the signed consent in person. The potential participant is encouraged to ask any questions during the consent process and anytime during his/her study participation. If preferred by the potential participant, s/he will directly contact the principal

investigator or co-investigator, for any questions or concerns. Prior to meeting with the coordinator in person, the potential participant will receive a consent form to review and will be given time to discuss this clinical study with anyone (including the PIs of this study) before making a decision.

Individuals with the reduced mental capacity (e.g., due to medication, drug abuse, injury or disease) are excluded from this study (see the fifth exclusion criterion above). Neurophysiological measures to be made in this study require the participant to be able to respond to the investigator's commands and questions during simple motor tasks, and therefore, individuals with known cognitive impairment will be excluded. This further excludes the individual who are not able to consent by him/herself.

Sharing Data: The RESTORE registry (Pro#00037803), from which this study may recruit subjects, also serves as a data analysis tool by which interdisciplinary teams may share data across projects and provide MUSC's stroke recovery research community with a more complete registry with key stroke elements. Some subjects may have participated or will participate in other stroke related research studies at MUSC. Sharing data from this and other stroke research studies with RESTORE will allow for more targeted recruitment efforts in the future and could reduce the burden placed on subjects by reducing the duplicative efforts of collecting common data and physical function assessments requested by multiple studies and storing them in one centralized and secure location.

Subjects are informed in the consent process if they enroll into the RESTORE registry, their data from this study will be shared. Those who have participated in other stroke research will be asked to sign a Release of Study Records form to share data with RESTORE if they did not already authorize release.

Subjects will be asked to sign a HIPAA authorization stating their health information may be disclosed to MUSC investigators requiring their data for their research projects upon approval by an Institutional Review Board.

9.0 Study Design / Methods

This study is a partial cross-over waitlist control design, in which each of the 20 participants post stroke will participate in 7 visits over a two-week period, during which measurements will be taken 10 times. Neurophysiological and functional measurements will be collected five times over 3 visits during the first week (treatment as usual control week), through which each participant will serve as their own "controls" for their second week of measurements. No sham or other treatment procedure will occur during this week. On the second week, all participants will transition to the DDN intervention week where five measurements will be collected over 3 visits (one pre-DDN baseline and four post-DDN measurements: immediately after, 90 minutes, 24 hours, and 72 hours).

Deep Dry Needling (DDN)

DDN procedures used in this project have been widely used in clinical practice to treat spasticity and pain in individuals with neurological and non-neurological (orthopedic) injuries [15,16,18,20,21,48,75].

Each participant receives a single session of DDN, targeting the medial gastrocnemius. In each DDN session, first, localized hypersensitive spots in palpable taut bands of the targeted skeletal muscles (i.e., MTrPs)(75, 76) are identified with pincer palpation. Then, after cleaning the skin area over a MTrPs with alcohol swabs, a disposable stainless steel acupuncture needle is inserted into the skin, penetrating approximately 15 to 20 mm to the depth of the trigger point, until the local twitch response (LTR) is elicited. Once the LTR is confirmed, the needle is moved up and down

(~4-5 mm vertically) with a small piston motions (approximately at 1 Hz for 25 to 30 seconds) with no rotation at the MTrPs (9,10, 38). The same procedure is repeated at other MTrPs in the same local skin region as needed until the LTR is eradicated. After removing the needle, the needled area is rubbed to prevent bleeding and bruising. Each participant will complete 5 repetitions of each of the following: ankle plantarflexion/dorsiflexion passive range of motion (PROM), sub-maximal concentric and eccentric contractions of the plantarflexors as would be typical in a clinical setting.

Electromyography (EMG) and nerve stimulation

At the beginning of each session, surface self-adhesive Ag-AgCl electrodes are placed over the TA, medial and lateral gastrocnemius (MG and LG), and soleus muscles of the studied leg. Throughout the study, all EMG activity is amplified, band-pass filtered (10-1000 Hz), sampled at 3,200 Hz, and stored. Nerve stimulation protocol consists of 4 components: (1) single pulse posterior tibial nerve stimulation for the triceps surae H-reflex / M-wave (H/M) recruitment curve measurement, (2) single pulse common peroneal (CP) nerve stimulation for the TA H/M recruitment curve measurement, (3) multiple pulse (train) tibial nerve stimulation for cutaneous reflex measurement, and (4) multiple pulse (train) superficial peroneal (SP) nerve stimulation for cutaneous reflex measurement.

- (1) ***Single pulse posterior tibial nerve stimulation for triceps surae H/M recruitment curve:*** To elicit the triceps H-reflex, the tibial nerve is stimulated in the popliteal fossa, using surface Ag-AgCl electrodes and isolated constant current stimulation. The stimulating electrode pair is placed so as to minimize the H-reflex threshold and to avoid stimulation of other nerves. For eliciting the H-reflex and M-wave, a 1-ms square stimulus pulse is delivered when the participant has maintained his/her natural standing level (typically, 10-20% of maximum voluntary contraction (MVC) level of EMG activity) of soleus EMG activity for at least 2 s. The minimum interstimulus interval is 5 s. An H/M recruitment curve is obtained by gradually increasing the stimulus intensity in increments of 1.2-2.5 mA from the H-reflex threshold to the maximum H-reflex (H_{max}) to an intensity just above what is needed to elicit the maximum M-wave (M_{max}) [77-79], while the participant stands and maintains the above noted level of soleus EMG activity. About 10 different intensities are used to obtain a recruitment curve, and four EMG responses are averaged to measure the H-reflex and M-wave at each intensity. Then, about 100 responses are elicited at the H_{max} level of stimulus intensity (i.e., weak to mild intensity) while monitoring cortical electroencephalographic (EEG) activity.
- (2) ***Single pulse common peroneal (CP) nerve stimulation for TA H/M recruitment curve:*** To elicit the H-reflex and M-wave in the TA, the CP nerve is stimulated at the neck of the fibula, using surface Ag-AgCl electrodes and isolated constant current stimulation. For eliciting the H-reflex and M-wave, a 0.5-ms square stimulus pulse is delivered when the participant has maintained his/her natural standing level of soleus EMG activity for at least 2 s, with the minimum interstimulus interval of 5 s. An H/M recruitment curve is obtained by gradually increasing the stimulus intensity from the H-reflex threshold to the H_{max} to an intensity just above what is needed to elicit the M_{max} [77-79], while the participant stands and maintains the above noted level of soleus EMG activity. About 10 different intensities are used to obtain a recruitment curve, and four EMG responses are averaged to measure the H-reflex and M-wave at each intensity. Then, about 100 responses are elicited at the H_{max} level of stimulus intensity (i.e., weak to mild intensity) while monitoring cortical EEG activity.
- (3) ***Train of tibial nerve stimulation for cutaneous reflexes:*** The distal tibial nerve is stimulated on the medial surface of the ankle posterior to the medial malleolus by trains of five pulses at 200 Hz, with a pulse width of 1.0 ms [34,80]. The stimulus electrodes are placed at a location at which strong radiating paresthesia is reported by the participant in the appropriate cutaneous

receptive fields (i.e., plantar surface of foot). While standing, the perceptual threshold, defined as the lowest stimulation detectable by the participant, and the radiating threshold (RT), defined as a clear radiating paresthesia, are determined. Perceptual threshold is thought to represent local activation of cutaneous receptors lying immediately underneath the recording electrodes, whereas RT is likely representing electrical activation of fascicles in the underlying cutaneous nerve [80,81]. 1×RT, 2×RT, and 3×RT of train of stimuli are delivered while the standing participant maintains the above described level of soleus EMG activity. Fifteen to 20 trials are averaged for each stimulus intensity, with the minimum inter-train interval of 5s.

(4) ***Train of superficial peroneal (SP) nerve stimulation for the cutaneous reflexes:*** The SP nerve is stimulated on the anterior surface of the leg just near the crease of the ankle joint by trains of five pulses at 200 Hz, with a pulse width of 1.0 ms [34,80]; the stimulus location at which the participant receives strong radiating paresthesia in the appropriate cutaneous receptive fields (i.e., foot dorsum). While standing, the perceptual threshold and the RT are determined. 1×RT, 2×RT, and 3×RT of train of stimuli are delivered while the standing participant maintains the above described level of soleus EMG activity. Fifteen to 20 trials are averaged for each stimulus intensity, with the minimum inter-train interval of 5s.

Analysis of H-reflex and cutaneous reflexes

The H-reflex and the M-wave amplitudes are measured as the peak-to-peak values in time windows determined for each participant. Typically, for the soleus, the H-reflex occurs in a time window of 30–50 ms post-stimulus 6–25 ms post-stimulus for the M-wave. For the MG, LG, and TA, the M-wave and H-reflex occur with shorter latencies [79]. For all muscles, the H_{max} , M_{max} , and H_{max}/M_{max} ratio are obtained from the recruitment curve measurement.

To analyze cutaneous reflexes, the background (prestimulus) EMG is subtracted from the post-stimulus EMG trace [34,78]. Then, subtracted EMG traces from each muscle are analyzed for peak reflex amplitudes at two distinct epochs termed early (~50–75 ms to peak) and middle (~75–120 ms to peak) latencies [78,83].

Assessment of sensory and motor function

Fugl-Meyer Assessment: Fugl-Meyer Assessment is one of the most widely used quantitative measures of motor impairment and recovery in post-stroke hemiparetic individuals. The assessment includes: motor function (upper extremity maximum score = 66; lower extremity maximum score = 34), sensory function (maximum score = 24), balance (maximum score = 14), joint range of motion (maximum score = 44), and joint pain (maximum score = 44). Each item is scored on a 3-point ordinal scale: 0 = cannot perform, 1 = performs partially, 2 = performs fully. The maximum score is 226.

10-meter walk test: The participant is asked to walk at his/her fastest comfortable speed on an indoor flat straight walkway that has markers at 0, 2, 12, and 14 m, 3 times. The 10-meter speed is calculated from when the toes of the leading foot cross the 2-m marker to when they cross the 12-m marker. An assistive device (e.g., walker) can be used. If the participant's device use changes during the study, the measurements will be made with both the new and old devices.

Modified Ashworth Scale: To measure spasticity, resistance to passive movement about a joint is tested at a range of velocities. The score ranges from 0-4 (i.e., 0: normal muscle tone; 4: rigid in flexion or extension [84]).

Visual Analog Scale for Pain: To measure pain, participants rate the level of pain they are experiencing in the affected limb. The score ranges from 0 to 10 (0="no pain" and 10="worst imaginable pain").

Range of Motion: Range of motion in the affected limb is measured using a standard

goniometer. Both passive and active range of motion will be recorded.

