Available small studies, case reports (14-22), and our preliminary data (87) support that DDN likely produces neural plasticity at both spinal and supraspinal levels. Thus, our central hypothesis is that ***DDN at MTrP induces plasticity in the spinal and supraspinal pathways and produces therapeutic effects.*** While the steady increase in therapeutic use of DDN implies its clinical potential, its optimal use is yet to be established, largely due to the limited mechanistic understanding of its neurophysiological effects. This pilot project is our first step towards understanding the neurophysiological mechanisms of DDN, specifically the spinal mechanisms of DDN-induced plasticity. This project evaluates these mechanisms via two specific aims:

Aim 1. To evaluate the effects of DDN on proprioceptive reflexes in people with spasticity due to stroke.

In people with spasticity the excitability of the H-reflex pathway (an electrical analog of spinal stretch reflex) becomes elevated and reciprocal inhibition of the plantarflexors by the dorsiflexors becomes impaired (25, 26). Thus, to investigate the effects of DDN at the medial gastrocnemius (MG) MTrP on excitatory and inhibitory proprioceptive reflexes, in 20 individuals with spasticity due to stroke we will measure the H-reflex – M-wave (H/M) recruitment curves and reciprocal inhibition in the triceps surae muscles before, immediately after, 90 minutes after, 24 hours after, and 72 hours after DDN. One week prior to DDN, the same measurements will be repeated 5 times, with inter-measurement intervals matching to pre and post DDN measurements. We anticipate that decreases in H-reflex size and reciprocal inhibition will occur between pre and post DDN time points.

Aim 2. To evaluate the effects of DDN on cutaneous reflexes in people with spasticity due to stroke. Modulation of cutaneous reflexes to non-noxious stimulation of the skin become abnormal

post-stroke, reflecting the altered somatosensory processing in this population (33, 34). Thus, in this project, we will examine cutaneous reflex responses to non-noxious stimulation of the distal limb (i.e., at or below the area treated with dry-needling) at the same time points as the proprioceptive reflexes before and after a single DDN session. We anticipate that cutaneous reflex amplitudes will be decreased after DDN.

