Additionally, to interpret these reflex changes related to typical clinical measures, we will measure passive and active dorsiflexion range of motion (ROM) and the Modified Ashworth scale, Fugl-Meyer, and 10-m walk test. These measurements will facilitate the development of future DDN clinical trials towards establishing spinal neurophysiological mechanisms of DDN.

The findings from this project would also help clinicians estimate when post DDN motor practice/training therapies should be administered for improving motor function in persons with and without spasticity. The data obtained through this pilot project will significantly strengthen our future NIH R-series applications, through which we plan to test the hypothesis that a single administration of DDN procedures will produce lasting effects on spinal neurophysiology that support temporary relief/alleviation of sensorimotor impairments in people with spasticity due to chronic stroke.

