In sum, the current view/presumption is that dry needling can help to restore the functional state of end plate and alleviate hypertonia and hyperalgesia through its immediate mechanical effects on end plate and by increasing the local blood flow and oxygenation. However, to date, its neurophysiological effects on spinal and supraspinal somatosensory processing in people after stroke are not yet understood. To determine the clinical utility of dry needling in treating spasticity and/or related sensorimotor disorders after stroke, it is essential to understand its neurophysiological impact on CNS pathways involved in sensorimotor function. Thus, the goal of this project is to characterize neurophysiological effects of dry needling on spinal and supraspinal somatosensory pathways in people with spasticity due to chronic stroke.

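### The control week is collected but no DDN-versus-control-week contrast is specified; secondarily, needling cannot be separated from the movement block inside the DDN procedure

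*Combined protocol and SAP*

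**What the plan says.** **Control week.** Section 9.0 says that measurements are taken "five times over 3 visits during the first week (treatment as usual control week), through which each participant will serve as their own" control for the second week. Aim 1 in section 1.0 matches the two weeks on measurement content and spacing: "the same measurements will be repeated 5 times, with inter-measurement intervals matching to pre and post DDN measurements". Week 2 then has one baseline and four later measurements: immediately after DDN, and at 90 minutes, 24 hours and 72 hours.

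**Analysis.** The data analysis paragraph of section 10.0 gives one method for comparing reflex sizes before and after needling. It is a two-way repeated measures ANOVA with factors side and time, followed by Bonferroni-corrected t-tests. The levels of time, the number of comparisons and the alpha are not given. No week or condition factor appears. The electrode description in section 9.0 covers the "medial and lateral gastrocnemius (MG and LG), and soleus muscles of the studied leg".

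**Movement block.** The last step under the DDN heading of section 9.0 reads: "Each participant will complete 5 repetitions of each of the following: ankle plantarflexion/dorsiflexion passive range of motion (PROM), sub-maximal concentric and eccentric contractions". The muscles contracted are the plantarflexors. Of the control week the same section says: "No sham or other treatment procedure will occur during this week".

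**Attribution.** Aim 1 is "to investigate the effects of DDN at the medial gastrocnemius (MG) MTrP on excitatory and inhibitory proprioceptive reflexes". Section 2.0 says that "the goal of this project is to characterize neurophysiological effects of dry needling on spinal and supraspinal somatosensory pathways".

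**The concern.** The control week supplies half of the ten measurements and is the design's only protection against change that would have occurred without DDN. Each measurement is itself a long session of nerve stimulation while standing, so a reflex could drift between measurements for that reason alone. A before/after test counts such drift as a DDN effect. The project is meant to support mechanistic claims and later grant applications, so an effect with the wrong label would be carried forward.

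The second matter is separate and smaller. The aims speak of needling at a trigger point, but what is delivered is needling plus a short set of ankle movements and contractions. A conclusion about needling alone would go beyond the data under any analysis.

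**Working it through.** The plan states no power, effect size, SD or alpha, so there is no figure of its own to reproduce.

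**1. What each comparison estimates.** Let N be the needling effect, M the effect of the movement block, and D1 and D2 the drift from repeated testing and time within week 1 and week 2.

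- Before/after in the DDN week: N + M + D2.
- DDN-week change minus control-week change: N + M + (D2 − D1).

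The week contrast removes the part of the drift common to both weeks. Neither quantity isolates N. These are therefore two different defects, and curing one does not cure the other.

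**2. Can the stated factors supply the contrast?** Section 9.0 describes recording on the studied leg, so side is not an evident substitute for the control week. Time might be read as all ten measurements, but even then no comparison of the two weeks' changes is named.

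**3. Measurement load common to both weeks.** The counts come from the nerve stimulation part of section 9.0. They are approximate because the plan says about 10 intensities and about 100 responses. I assume that every component is run at every measurement.

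- Single pulses: 2 nerves × (10 × 4 + 100) = 280.
- Trains: 2 nerves × 3 intensities × 15 to 20 = 90 to 120.
- Total: 370 to 400. At the 5 s minimum spacing this is 370 × 5 / 60 = 30.8 min to 400 × 5 / 60 = 33.3 min.

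This load precedes the second measurement in both weeks. If the first three measurements share a visit, the load before the 90-minute one is 740 to 800 stimuli, or 61.7 to 66.7 min. Reciprocal inhibition, threshold finding and the functional tests are not counted.

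**4. Consequence of drift for a before/after test (illustration).** Paired t-test, n = 20, no DDN effect. The assumed shift is in SDs of the change score.

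| Shift | Significant at 0.05 | Significant at 0.0125 (0.05/4) |
|---|---|---|
| 0.2 | 13% | 5% |
| 0.3 | 25% | 10% |
| 0.5 | 56% | 33% |
| 0.8 | 92% | 78% |

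If the same drift occurs in both weeks, it cancels in the week contrast by construction, and the test keeps its nominal level.

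**5. Precision cost of the week contrast.** With equal weekly variances and correlation rho between the two weekly changes (not given in the documents), the SD of the difference is SD × √(2(1 − rho)). With 19 degrees of freedom, t = 2.093 at 95%, so the before/after half-width is 2.093/√20 = 0.468 SD. At 0.0125, t = 2.759 and the half-width is 0.617 SD. For 80% power, before/after needs a shift of 0.66 SD at alpha 0.05.

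| rho | Width ratio | 95% half-width (SD) | Half-width at 0.0125 (SD) | Shift for 80% power, alpha 0.05 (SD) |
|---|---|---|---|---|
| 0 | 1.41 | 0.66 | 0.87 | 0.93 |
| 0.3 | 1.18 | 0.55 | 0.73 | 0.78 |
| 0.5 | 1.00 | 0.47 | 0.62 | 0.66 |
| 0.7 | 0.77 | 0.36 | 0.48 | 0.51 |

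The contrast is the more precise of the two once rho exceeds 0.5. A negative rho would make it worse than 1.41.

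**6. Movement block.** Its absence from week 1 is inferred: it stands under the DDN heading, no section schedules it in week 1, and section 9.0 rules out other treatment procedures then. That it comes before the measurement immediately after DDN is inferred from sentence order and is not stated.

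**The case against.** The best defence on the main point is that time was meant to span all ten measurements and that a week comparison would follow naturally. That may be the intention, but the plan does not commit to it. Section 10.0 frames the question as before versus after needling.

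On the movement block, the defence is stronger. The protocol presents the block as typical of clinical practice and places it inside the procedure, so DDN can fairly be read as the whole package. Both weeks also contain range-of-motion, Ashworth and walking tests and long standing, so the added movement may matter little. All of this stands, and it reduces the point to one of wording.

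Four stronger readings are tempting and are not supported:

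- A reader might infer that the unmatched block and the missing contrast together limit the results to needling plus movement. The missing contrast plays no part in that limit. With it, needling and movement remain inseparable. Without it, even the package is not separated from drift.
- A reader might take the stimulus counts as the size of the movement problem. They describe measurement load present in both weeks, not the block.
- A reader might suppose that findings at 24 or 72 hours are less exposed to a movement effect. No section gives the duration of such an effect.
- Section 1.0 hopes the results will "help clinicians estimate when post DDN motor practice/training therapies should be administered for improving motor function", and a reader might see a contradiction with movement inside the session. A few sub-maximal repetitions need not be the practice or training meant there.

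**Conclusion.** The main point holds: the control week is collected as each participant's own control, but the stated reflex analysis does not use it as one. The size of any drift is unknown. The 25% and 56% figures rest on assumed shifts of 0.3 and 0.5 SD and on a paired t-test standing in for the post-hoc test. The precision figures rest on n = 20, equal weekly variances and an assumed rho. The week contrast removes only drift common to both weeks; fixed week order and expectation remain uncontrolled, since there is no sham and every participant has the control week first.

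The movement point holds as a lower-severity limit on wording. An effect of the whole procedure is a defensible target if it is named as such. The documents do not show that the movement has an effect, and none is claimed here.

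**What to change.** **Main change, section 10.0.** Make the main reflex analysis a within-participant week × time analysis on the studied leg. Drop the side factor, or keep it as secondary if both legs are measured. The main contrast is DDN-week change from baseline minus control-week change from baseline at each of the four matched post times. Name the main reflex outcome for each aim (for example Hmax/Mmax for Aim 1), and apply Bonferroni over the four times for each. Keep before/after as descriptive. Report the between-week correlation for planning later studies.

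The cost is one analysis paragraph, using data already to be collected. The interval is up to 1.41 times the before/after width if weekly changes are uncorrelated (wider still if negatively correlated), equal at rho = 0.5 and narrower above that.

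**Secondary change, sections 1.0 and 2.0 and the eventual conclusions.** Describe the effect as that of the DDN procedure as delivered, including the movement block, and not of needling at the trigger point alone. State when the block occurs relative to the first post-DDN measurement. This changes wording only, leaves the procedure as it is, and narrows the claim.

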5.0 Number of Subjects

Twenty adults (≥ 18 years old) with spastic hyperreflexia due to stroke are recruited from the community around the MUSC and a greater Charleston area.

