10.0 Data Management

Data analysis: Reflex sizes are calculated in reference to each participant's M_{max} measured during natural standing. For example, the peak-to-peak H-reflex amplitude is normalized to the peak-to-peak M_{max} amplitude, and the mean rectified H-reflex amplitude is normalized to the mean rectified M_{max} amplitude.

For comparing reflex sizes before and after dry needling, a two-way repeated measures ANOVA (studied side of the extremity \times time) will be used, together with Student t-test with Bonferroni correction as a post-hoc test. For simple comparison between participants without known neurological conditions and participants after stroke (e.g., age and M_{max}), and assessments of changes in sensory and motor function (i.e., only applicable to participants after stroke), a Student t-test will be used.

Data management: The data will be managed by the PIs and research coordinator at the College of Health Professions (CHP). All EMG and assessment data are electronically stored in the secure CHP server with password protection. Only the investigators directly involved in this project have access to these data.

Protection of participant confidentiality is essential in human clinical trials. The participants' confidential information will be securely stored in locked cabinets of a locked room and a password-protected computer, and only the principal and co-investigators and the research coordinator will have access to the participant's confidential information. For the length of the study, limited personal information (specifically, the participant's name, address, and social security number) will also be accessible to the program administrator for processing the participant reimbursement paperwork. Investigators and therapists, who run data collection sessions, will have access to the EMG and other collected data for the purpose of analysis, but will have no access to the participant's confidential information. Alphanumeric codes will be assigned to each participant's dataset to protect confidentiality.

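### Session staff receive the EMG for analysis, and the protocol describes no masking of week or time point, no locking of H/M windows across the 10 recordings and no peak or polarity rule for cutaneous responses

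*Combined protocol and SAP*

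**What the plan says.** **Scoring.** Section 9.0 (Analysis of H-reflex and cutaneous reflexes) states: "The H-reflex and the M-wave amplitudes are measured as the peak-to-peak values in time windows determined for each participant". Limits are given only as typical values for soleus: 30–50 ms for the H-reflex and 6–25 ms for the M-wave. For MG, LG and TA the text says only that latencies are shorter, although MG is the needled muscle. For cutaneous reflexes, background EMG is subtracted and the traces are "analyzed for peak reflex amplitudes at two distinct epochs termed early (~50–75 ms to peak) and middle (~75–120 ms to peak) latencies".

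**Who holds the data.** Section 10.0 states: "Investigators and therapists, who run data collection sessions, will have access to the EMG and other collected data for the purpose of analysis". Section 11.0 repeats this. On coding, both sections say: "Alphanumeric codes will be assigned to each participant's dataset to protect confidentiality".

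**Design and expectation.** Section 9.0 places the control week first for everyone and adds: "No sham or other treatment procedure will occur during this week". Section 1.0 predicts a direction for both aims: "We anticipate that decreases in H-reflex size and reciprocal inhibition will occur between pre and post DDN time points" and "We anticipate that cutaneous reflex amplitudes will be decreased after DDN".

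**Size and analysis.** Section 5.0: "Twenty adults (≥ 18 years old) with spastic hyperreflexia due to stroke are recruited". Section 9.0 gives 10 measurements per participant, five in each week. Section 10.0 plans a two-way repeated measures ANOVA with Bonferroni-corrected t-tests. It states neither alpha nor the number of post-hoc comparisons.

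**The concern.** Participants and session staff cannot be masked, because there is no sham and needling always falls in the second week. Scoring of the stored traces is the one stage that could be masked, and the protocol describes nothing to that end. The codes hide who the participant is, but nothing is said to hide which week or time point a trace comes from.

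Three conditions therefore coincide. People who know the condition have the traces for analysis, some scoring steps are left open, and the hoped-for direction is declared. The control week gives no protection, since a scorer who knows the week can treat the two weeks differently. Mmax is also read in participant-specific windows and is the reference for reflex size (Section 10.0), so window choice can affect both parts of the ratio. What is at stake is whether a reported fall in reflex size can be separated from how the traces were read.

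**Working it through.** **Step 1. What is left open, by outcome**

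| Outcome | What is specified | What is not |
|---|---|---|
| H-reflex, M-wave, Hmax/Mmax | Peak-to-peak value, window set per participant, four responses averaged per intensity | Who sets the window, by what rule, from which recordings, and whether it is the same in all 10 |
| Cutaneous reflexes | Peak in two approximate epochs common to all participants, 15–20 trials averaged per intensity | Exact epoch limits (the two meet at about 75 ms), how the peak is chosen, how its sign is handled |

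A peak-to-peak value in a fixed window is a maximum minus a minimum, so if the window is locked there is little left to judge. A background-subtracted cutaneous trace can go above or below zero. With soft epoch limits and no polarity rule, choosing the peak can involve judgement. The cutaneous peaks are therefore the more exposed outcome.

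**Step 2. How much a scoring shift would matter**

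The documents give no scoring error, SD, alpha or power, so there is no figure of theirs to reproduce. What follows is illustration only.

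Inputs:
- n = 20 pairs (Section 5.0), so df = 19.
- Assumed: no true effect, and a systematic scoring shift toward a decrease of d = 0.1, 0.2 or 0.3 SD of the paired change.
- Assumed: a two-sided paired t-test at alpha 0.05, and at 0.05/4 = 0.0125 for Bonferroni over the four post-versus-pre comparisons in the DDN week.

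Formula: noncentrality λ = d√n. Rejection probability = P(T > c) + P(T < −c), where T is noncentral t with df 19 and noncentrality λ, taking a decrease as positive. The critical value c is 2.093 at 0.05 and 2.759 at 0.0125.

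| Shift d | λ = d√20 | Reject at 0.05, total (false decrease) | Reject at 0.0125, total (false decrease) |
|---|---|---|---|
| 0 | 0 | 5.0% (2.5%) | 1.25% (0.6%) |
| 0.1 | 0.447 | 7.1% (6.2%) | 2.0% (1.9%) |
| 0.2 | 0.894 | 13.6% (13.4%) | 4.8% (4.7%) |
| 0.3 | 1.342 | 24.7% (24.7%) | 10.3% (10.3%) |

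Bonferroni correction lowers the absolute rates but does not remove the inflation. At a shift of 0.2 SD, total rejection is 13.6/5 = 2.7 times nominal at 0.05 and 4.8/1.25 = 3.8 times nominal at 0.0125.

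**The case against.** A reader might infer that session staff themselves set the windows, that windows are reset at each recording, or that scoring will in fact drift toward a decrease. The documents support none of these. Section 10.0 grants access for analysis and does not say who sets windows. Section 9.0 sets H/M windows per participant, not per recording, and the cutaneous epochs are common to everyone. Nothing in the documents shows drift. The amplitudes are averages, and the reflexes are referenced to Mmax. All of that stands, and it is why Hmax/Mmax is less exposed. What remains is that the text never says the window is locked or chosen without knowledge of the time point.

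It is also fair to object that the shifts in the table are arbitrary, and that an uncorrected 5% test is not the planned one. The 0.0125 column partly answers the second objection, but four comparisons is itself an assumption and the ANOVA is not modelled. The table shows that small drift would matter at n = 20, not that it is likely.

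An obvious remedy also has a trap. Tuning windows and polarity on control-week recordings alone could fit that week's noise and favour larger control-week amplitudes, which is a bias toward the expected decrease when the weeks are compared. Fixing polarity in advance could mis-score a true reversal after DDN. The fix below avoids both.

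Finally, locked windows applied by script already remove much of the discretion, so masking then adds less. It still covers the setting of the windows and any manual exception.

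**Conclusion.** The concern holds in a limited form. The protocol gives session staff the EMG for analysis, codes by participant only, masks neither week nor time point, does not say that the H/M windows are locked across the 10 recordings, and has no peak or polarity rule for cutaneous responses. In an unshammed, fixed-order design with a predicted decrease, this is avoidable room for scoring bias in both aims, greatest for the cutaneous peaks.

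Its size cannot be estimated from the documents. The illustrative range is about 7% to 25% rejection at two-sided 0.05 and about 2% to 10% at 0.0125. It rests on 20 complete pairs, no true effect, assumed shifts of 0.1 to 0.3 SD, and an assumed alpha and number of comparisons. This is a cheap improvement to make, not evidence that the results will be wrong.

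**What to change.** Add to Sections 9.0 and 10.0:

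1. Give each participant's 10 stored recordings random file codes that hide week and time point.
2. Have the existing analyst set each participant's windows once, by a written rule, from all of that participant's coded recordings pooled and not from the control week alone.
3. Apply the windows unchanged to all 10 recordings by script.
4. Score cutaneous responses as signed amplitudes, so that a reversal is kept.
5. Log every exception, and unmask only after the amplitude file is locked.

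The cost is a few sentences and a little scripting. It needs no sham, visit, participant or extra reader, and it can be applied to traces already stored. The downside is that windows cannot be re-tuned for a single recording without a log entry.

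Masked scoring does not remove effects that arise while recording unmasked: electrode placement at each session, choice of stimulus intensities, and determination of the radiating threshold. State these as a limitation.
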